10.5.3.4. Known-Groups Validation

Known-groups validity will be estimated at baseline only. Known-groups validators will consist of the PGI-S (both respiratory and fatigue for the QOL-B respiratory and PROMIS F-SF7a, respectively) and a median split on reported ppFEV₁. Known-groups validity will be estimated by fitting a linear model to the PRO score(s) at baseline and contrasting marginal means LSMEANS across known-group validator levels. Known-groups contrasts will consist of comparing the low-severity PGI-S group (reference) against all other PGI-S groups (effect) and the ppFEV₁ < median group (reference) against the ppFEV₁ ≥ median group (effect) in pairwise contrasts.

10.5.4. Longitudinal Validation

Longitudinal validation will consist of both test-retest reliability (conducted pre-exposure between screening and baseline) and within-subject meaningful change (conducted between baseline and EOS (Month 7)).

10.5.4.1. Test-retest Reliability

Test-retest reliability correlations will be based on the 2-way random ICC ([Shrout and Fleiss, 1979](#)). Test-retest reliability estimates of 0.7 and above will indicate satisfactory retest reliability.

Test-retest reliability will be assessed in a group of subjects reporting no change over the retest interval. In this case, a 30-day retest interval occurring between screening and baseline will be used for TRTR. A symptomatically stable retest sample will be defined among subjects

experiencing no change on the PGI-S between Baseline and follow-up (PGI-S change score is zero).

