3.3. Study Duration

Subjects will receive ALIS + background regimen or ELC + background regimen for 6 months and then remain off all study drugs for 1 month. The Screening period will be up to approximately -70 days to -1 day (~2.5 months).

The total duration of the study will be up to 9.5 months from the Screening visit to EOS.

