4.2.5. Subject Rescreening Procedures

Upon approval by Sponsor, subjects may be rescreened once, if the following apply:

- The screening culture is not positive for MAC, or
- The subject has a MAC isolate with MIC for amikacin ≥ 128 $\mu\text{g/mL}$ at Screening, and/or
- The average QOL-B respiratory domain score is > 85 , and/or
- The subject has active COVID-19 infection.

Subject will only be allowed to be rescreened if all other entry criteria have been satisfied. If a subject's average QOL-B respiratory domain score is > 85 , the subject may take the

questionnaire again, once on the next day and again within 7 days to calculate a new average; all other Screening assessments do not have to be repeated. Subjects should be rescreened within the original screening period timeframe (approximately -70 to -1 days).

If a subject is rescreened due to Screening culture that is not positive for MAC or MAC isolate has amikacin MIC \geq 128 μ g/mL, all other Screening assessments must be repeated. The subject will have a new Screening window (approximately -70 to -1 days).

If a subject has active COVID-19 infection, the subject may be rescreened once recovered and the diagnostic tests are negative. All Screening assessments must be repeated. The subject will have a new Screening window (approximately -70 to -1 days). Subjects who experienced COVID-19 related hospitalization, severe disease, and/or ARDS may not be rescreened.

Rescreened subjects will be assigned a new subject number within the EDC system.

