6. STUDY PROCEDURES

6.1. Schedule of Assessments

The Schedule of Assessments is presented in [Table 4](#).

COVID-19 restrictions and/or concerns may impact subject attendance at in-clinic visits (Section 6.3). In the event subjects are restricted from attending in-clinic visits or if subjects have concerns regarding travel and attending in-clinic visits (due to potential public health concerns), the site should contact the Sponsor on how to conduct the scheduled assessments, and decisions should be documented in the source documentation.

The PRO instruments will be provided to the subject in electronic format on a computer tablet and should be conducted at approximately the same time of day at the specified timepoints.

All PRO assessments must be completed prior to other study assessments (eg, physical examination, vital signs, laboratory assessments, audiology, etc) with the exception of sputum collection. If the subject produces their best sputum samples first thing in the morning prior to being able to attend a clinic visit, the subject should consistently collect sputum samples first, then proceed with PRO assessments throughout the study.

At each in-clinic visit, the subject will complete the PRO assessments in the order listed below. The approximate time to complete each assessment is provided; these are conservative estimates based on different studies and actual time may be less than indicated.

1. QOL-B (~10-15 minutes)
2. PROMIS F-SF 7a (~8-12 minutes)
3. EXACT (~3 minutes)
4. EXACT-RS (~3 minutes)
5. SGRQ (~10 minutes)
6. FACIT– Fatigue (~8-12 minutes)
7. PGI-S– Respiratory (~1 minute)
8. PGI-S– Fatigue (~1 minute)

All remaining assessments must be completed prior to administration of study drugs. If additional assessments for monitoring are recommended per local labeling guidance, the site should complete unscheduled assessments.

Table 4: Schedule of Assessments

INS-415	Screening	Treatment Phase						
		In-Clinic		Non In-Clinic ^a	In-Clinic	Non In-Clinic ^a	In-Clinic	
		Baseline/ Day 1	Month 1	Month 2	Month 3, 5	Month 4	Month 6 (EOT) ^b	Month 7 (EOS) ^c
		(V1)	(V2)	(V3)	(V4)	(V5, 7)	(V6)	(V8)
Visit Window	Approximately -70 days to -1 day	--	(±7)	(±7)	(±7)	(±7)	(±7)	(±7)
Informed consent	X	--	--	--	--	--	--	--
Pregnancy test ^d	X	X	X	X	X	X	X	X
Randomization	--	X	--	--	--	--	--	--
QOL-B ^e	X	X	--	--	X	--	X	X
PROMIS F-SF 7a ^e	X	X	--	--	X	--	X	X
EXACT ^e	X	X	--	--	--	--	--	X
EXACT RS ^e	X	X	--	--	--	--	--	X
SGRQ ^e	X	X	--	--	--	--	--	X

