Sites are strongly discouraged from performing local mycobacterium sputum cultures for the duration of the study, as this may introduce bias to subject assessments. Sputum may be sent to local laboratories to be cultured for organisms other than mycobacterium.

Microbiological Assessment

Sputum specimens will be cultured in broth media (liquid) in addition to agar media (solid), and will be held for up to 6 weeks. A negative culture result will not be reported until after this time has transpired. All contaminated samples will be retreated and re-cultured once.

Growth of other bacteria due to co-infections (eg, *Pseudomonas aeruginosa*, *M. abscessus*, other NTM) will be reported as applicable. Colony counts of MAC growth will be reported. Isolates of MAC will be identified using a commercial RNA probe (AccuProbe, Gen Probe, Inc., GenoType NTM-DR Ver 1.0, Hain Lifescience) and subsequently identified to species using molecular

methodology (Cousins et al., 1996). Standard antibiotic sensitivity testing using MICs will be routinely performed on mycobacterial isolates (CLSI, 2018a; CLSI, 2018b; Forbes et al., 2008).

The MAC species and genotype at the Screening and/or Baseline sputum specimen will be identified by whole genome sequencing (Illumina Nextseq500TM) in subjects who achieve sputum culture conversion and who subsequently have positive sputum culture(s) (broth or agar); typing by whole genome sequencing will also be conducted.

MAC Culture Assessment Definitions

MAC culture negative	No MAC growth on agar media and broth media in all sputum cultures at a visit.
Non-productive	Prior to culture conversion or post recurrence: visits where subjects were recorded as non-productive are considered MAC culture positive. Post culture conversion: visits where subjects were recorded as non-productive are considered MAC culture negative.
Culture conversion	No MAC growth on agar media and broth media in all sputum cultures at 2 consecutive visits. The date of conversion is defined by the date of the first of 2 consecutive negative cultures.
Recurrence: Relapse	Subsequent to culture conversion, at least 1 MAC positive culture in agar media or positive cultures in broth media in at least 2 consecutive visits. A MAC positive culture is defined as the same species and genome as cultured at Screening/Baseline.

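### The stated 30-day test-retest interval does not match a Screening period of up to about 70 days, and the PGI-S stability rule beside it names the wrong pair of visits

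*Protocol*

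**What the plan says.** Protocol 10.5.4.1 bases test-retest reliability on a two-way random ICC in subjects who report no change over the retest interval, with 0.7 as the threshold for satisfactory reliability. It then makes two specific statements.

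- On the interval: "a 30-day retest interval occurring between screening and baseline will be used for TRTR".
- On stability: "A symptomatically stable retest sample will be defined among subjects" who are "experiencing no change on the PGI-S between Baseline and follow-up (PGI-S change score is zero".

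On Screening, Protocol 3.3 says: "The Screening period will be up to approximately -70 days to -1 day (~2.5 months". The synopsis and Table 4 give the same range.

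Table 4 schedules the QOL-B, PROMIS F-SF 7a and both PGI-S items before dosing at Screening and Baseline only. The next administration of each is at Month 3, on treatment.

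The primary endpoint (Protocol 2.1), Protocol 1.3.3 and 10.5.2, and SAP 3.1 and 5.1 all place both the retest and the PGI-S stability condition between Screening and Baseline. Protocol 10.5.4 adds that the retest analysis is done before exposure. The SAP gives no interval length and leaves validation methods to the Validation Analysis Plan (VAP).

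**The concern.** A retest ICC can be interpreted only with its interval. Over a few days it reflects mainly measurement error. Over many weeks in untreated infection it also absorbs real change in symptoms. The QOL-B and PROMIS F-SF 7a each ask about roughly the past week, so two administrations ten weeks apart describe quite separate periods. If the pairs span 1 to about 70 days, a result reported as a 30-day ICC is mislabelled, and it is compared with a fixed 0.7 cut-off without saying what mix of intervals produced it.

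The stability wording is a separate fault. Baseline is a named visit in this protocol (Day 1), so a PGI-S change from Baseline to follow-up is a change after treatment starts. Selecting on it would not match the pre-exposure interval over which the ICC is computed.

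A smaller gap concerns repeat questionnaires. Under Protocol 4.2.5, a subject whose average QOL-B respiratory score exceeds 85 may take the "questionnaire again, once on the next day and again within 7 days to calculate a new average", and the other Screening assessments need not be repeated. Such a retake may have no PGI-S beside it. Neither document says which administration enters the ICC.

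**Working it through.** **1. Reproduce the plan's durations.** Inputs: 70 days of Screening (Protocol 3.3), 7 months from Baseline to end of study (Protocol 3.1), and a 28-day month (SAP 7.6.1).

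- Screening: 70 / 28 = 2.5 months, as stated.
- Total: 2.5 + 7 = 9.5 months, which matches "The total duration of the study will be up to 9.5 months from the Screening visit to EOS".
- With a 30.44-day month the figures would be 2.3 and 9.3.
- With 30 days of Screening the total would be 30 / 28 + 7 = 8.1 months.

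The protocol's own duration therefore assumes a Screening period of up to 70 days.

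**2. Interval implied by Table 4.** The Screening window is "Approximately -70 days to -1 day" and Baseline is Day 1. There is no Day 0 (SAP 7.6.2), so Day -1 to Day 1 is 1 day and Day -70 to Day 1 is 70 days. The interval runs from 1 to about 70 days, up to 70 / 30 = 2.3 times the stated figure. The 30-day figure does not reproduce. Neither document gives the distribution of intervals within that range.

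**3. Stability period.**

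| Source | Period for no PGI-S change |
|---|---|
| Protocol 2.1 (primary endpoint) and 1.3.3 | Screening to Baseline |
| Protocol 10.5.2 | Screening to Baseline |
| SAP 3.1 and 5.1 | Screening to Baseline |
| Protocol 10.5.4.1 | Baseline to follow-up |

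Protocol 10.5.4 also describes the retest as pre-exposure. Protocol 10.5.4.1 stands alone.

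**4. Illustrative effect on the ICC.** None of these inputs is in the documents: an ICC of 0.80 at 30 days, measurement reliability R (the ICC at zero interval), and exponential decay of the stable component. The model is ICC(t) = R × (0.80 / R)^(t/30).

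| R | ICC at 70 days |
|---|---|
| 0.85 | 0.85 × (0.9412)^2.333 = 0.74 |
| 0.90 | 0.90 × (0.8889)^2.333 = 0.68 |
| 0.95 | 0.95 × (0.8421)^2.333 = 0.64 |

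For R = 0.90, the curve reaches 0.7 at 30 × ln(0.7/0.90) / ln(0.80/0.90) = 64 days.

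The pooled ICC is closer to an average over the intervals present. For R = 0.90 the daily decay rate is k = -ln(0.8889)/30 = 0.003926. The average over intervals uniform on 1 to 70 days is 0.90 × (e^(-k) - e^(-70k)) / (69k) = 0.90 × (0.9961 - 0.7597) / 0.2709 = 0.79.

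**The case against.** Several points on the other side stand.

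**The stability phrase is unlikely to be followed literally.** Protocol 10.5.4.1 itself first refers to no change over the retest interval and places that interval between Screening and Baseline. The SAP prevails where it differs from the protocol (SAP 2) and says Screening to Baseline. A reader might infer that the stable sample will be picked on post-treatment response. The documents taken together do not support that, and Baseline to follow-up may be generic retest language. It still needs correcting. SAP Table 9, which lists changes to the protocol's analyses, does not mention it.

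**Long intervals are permitted, not shown to be typical.** A reader might infer from the culture rule in Protocol 8.1 (specimens "will be held for up to 6 weeks") that most subjects wait more than 30 days. However, the next sentence there ties that hold to the reporting of negative results, and enrolled subjects need a positive Screening culture. Susceptibility results are also needed for eligibility, but no turnaround time is given.

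**The retakes are a narrow case.** They arise only when the average score exceeds 85, they involve the QOL-B alone, and nothing says they enter the ICC.

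**The VAP is not among the documents.** It may set a window around 30 days. If so, unrestricted pooling is not the plan. The protocol text would still need to agree with it.

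**Requiring no PGI-S change is a partial safeguard.** It applies over each subject's own interval, whatever its length. A five-level item still leaves room for real change within a category.

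**Conclusion.** Both statements in Protocol 10.5.4.1 are wrong as written, and both bear on the primary endpoint. The retest interval is variable, from 1 to about 70 days, and the SAP does not correct the 30-day figure. The stability period should be Screening to Baseline, as the other sections say.

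A reader might infer that the ICC will fall below 0.7 because of long intervals. That is possible but not shown. In the illustration, a sample in which everyone waited 70 days would give about 0.64 to 0.74 across reliability 0.95 to 0.85, on either side of the criterion. With reliability 0.90 and intervals spread evenly over 1 to 70 days, the average is about 0.79, which passes. The answer turns on an interval distribution that the documents do not give, on an assumed decay model, and on an assumed 30-day ICC of 0.80. The illustration also ignores the restriction to subjects with unchanged PGI-S. Sample size and power are unaffected.

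**What to change.** In the protocol, and in the VAP if it repeats the text:

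1. Define the stable sample as PGI-S change of zero between Screening and Baseline, using the respiratory item for the QOL-B and the fatigue item for the PROMIS F-SF 7a.
2. Replace the 30-day interval with the actual one: variable, up to about 70 days.
3. Keep the ICC on all stable pairs as the main estimate and report the distribution of intervals beside it.
4. Add a prespecified sensitivity ICC by interval length, for example up to 30 days versus longer. The split is only an example; nothing in the documents fixes it. Restricting the main ICC to a narrow window is not needed and would discard an unknown number of pairs.
5. State that the pairs are the scheduled Screening and Baseline administrations with a matching PGI-S, not QOL-B retakes.

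The cost is a wording change and slightly more analysis. No new data are needed, because the visit dates are already recorded.

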10.5.4.2. Within-Subject Meaningful Change

Meaningful within-subject change will be estimated via change scores computed between Baseline and EOS (Month 7). Meaningful within-subject change will be characterized via point estimates obtained from the mean and median change score associated with the minimal improvement anchor group.

The point estimates will be examined by generating eCDFs and ePDFs stratified on PGI-S change and culture conversion anchor groups. The separation of eCDFs and ePDFs at the meaningful change point estimates will be contrasted to assess separation between the minimal improvement and no-change anchor groups.

10.5.5. Item-level Validation

Item-level analogs of the analyses outlined above will also be conducted to provide a comprehensive set of validation evidence for FDA review.

10.6. Other Efficacy Analyses

10.6.1. Secondary Efficacy Endpoint Analyses

Summaries of efficacy data will be presented by treatment group and by visit, as appropriate.

Reporting of categorical secondary endpoints will include basic statistics, estimates derived via logistic regression and will include estimates of proportions, and difference of proportions, together with corresponding 95% CIs resulting, as appropriate.

Reporting of continuous secondary endpoints will include basic statistics, estimates derived from ANCOVA model with change from baseline as response variable and treatment and baseline as independent variables, and will include estimates with corresponding 95% CIs as appropriate.

ANCOVA and logistic regression models may not include adjustment for randomization strata due to expected small counts within each combination of strata.

Time to culture conversion will be plotted via Kaplan-Meier method.

10.6.2. Exploratory Efficacy Analyses

All of the summaries pertaining to exploratory endpoints will utilize available data, unless otherwise stated in the SAP. Summaries will be presented by treatment group and by visit, as appropriate.

Difference between treatment groups in change from baseline to Month 7 in the QOL-B non-respiratory domains (physical, role, vitality, emotional, social, health perception) will be summarized. The data will be reported by timepoint and as change from baseline. Summary statistics estimates for means and difference between treatments together with corresponding 95% CIs will be provided.

Difference in proportion of subjects meeting that within-subject meeting meaningful change from baseline criterion from Baseline to EOT and Month 7 in PRO (as assessed QOL-B and PROMIS F-SF 7a) will be evaluated.

Note: The threshold for the criterion will be estimated via quantitative longitudinal analyses and will be available at the time of the analysis (post-unblinding).

Actigraphy data will be collected continuously throughout the study. For the purpose of analysis, mean activity and sleep efficiency will be derived at the protocol specified visits. The data will be reported by timepoint over time. Summary statistics estimates for means and difference between treatments together with corresponding 95% CIs will be provided.

Correlation between PRO respiratory domain mean responses and colony microbiology data will be explored.

Exploratory analyses may be conducted in selected subgroups of the population or pertaining to an exploratory question of interest defined in the SAP.

10.7. Safety Analyses

Safety summaries will utilize safety analysis data set and will be provided by treatment group on available data. Descriptive statistics will be provided.

10.7.1. Extent of Exposure

The exposure data will be summarized descriptively by treatment group (separately for each medication, total as randomized) and will include total number of doses of each medication received (ALIS/ELC, AZI, ETH) and duration of exposure. The amount of medication taken and used for these summaries will be based on the pill count of returned medication.

10.7.2. Concomitant Medications and Prior Therapy

Concomitant medications are those medications taken on or after the first dose of study drugs. Prior medications are those medications taken before the first dose of study drugs. A medication that starts prior to first dose but continues after the first dose of study drugs is classified both in prior and concomitant medications. Any medications taken for MAC lung infection or COVID-19 prior to Screening will be recorded. Non-study drugs taken 1 month prior to Screening and during the study will be recorded. Prior and concomitant medications will be summarized separately and will be mapped to an ATC class and Preferred Name using the WHO Drug Dictionary. These summaries will present the number and percentage of subjects using each medication. Subjects may have more than one medication per ATC class and Preferred Name. At each level of subject summarization, a subject is counted once if he/she reported one or more medications at that level. Each summary will be ordered by descending order of incidence of ATC class and preferred name within each ATC class.

Prohibited medication will be reported as part of concomitant summaries and as protocol deviation summaries if appropriate.

Data will be summarized descriptively by treatment over study duration.

10.7.3. Adverse Event Analyses

Adverse events will be coded using MedDRA by system organ class and preferred term. The severity of AEs will be graded to either mild, moderate, or severe.

The number and percent of subjects with AEs will be presented by treatment group. The severity of AEs, the relationship to study drugs (ALIS/ELC, AZI, ETH), AEs leading to study discontinuation, TEAEs, AESIs, and SAEs will be similarly presented. Treatment-emergent and treatment-related AEs will be tabulated by system organ class and preferred term.

10.7.4. Clinical Laboratory Evaluation Analyses

The results of hematology, blood chemistry, and urinalysis will be tabulated by treatment group. Laboratory values outside the normal ranges will be flagged. Subjects experiencing ALT or AST $\geq 3^*$ ULN and total bilirubin $> 2^*$ ULN according to Hy's Law will be listed.

Summary statistics (mean, median, range, change from Baseline) by treatment will be provided for each timepoint, as appropriate.

Baseline value is defined by laboratory results collected prior to first study drugs administration.

10.7.5. Vital Sign Analyses

Systolic and diastolic BP, pulse rate, RR, oxygen saturation, and body temperature will be listed for each subject. If applicable, summary statistics (mean change, percentage change from Baseline, and absolute change from Baseline) by treatment at each time point will be provided. Baseline value is defined as vital signs collected prior to the first dose of study drugs on Day 1/Baseline.

10.7.6. Physical Examination Analyses

Postbaseline abnormal findings of the physical examinations that meet the criteria of AEs will be included within AE reporting.

10.7.7. Audiology Analysis

Audiology test results and the change from Baseline will be summarized.

10.7.8. Other Safety Analyses

C-reactive protein value will be summarized descriptively by visit including changes from baseline.

Additional safety analyses may be specified in the SAP as appropriate.

